### 5.3 Prohibited Medications and Therapy

---

Except as listed in the eligibility criteria, the following medications are prohibited throughout the duration of the study:

- All biologics or small molecule medication (e.g., JAK inhibitors, sphingosine-1-phosphate [S1P] receptor modulators) with potential impact on UC
- Initiation of oral aminosalicylates, immunomodulators, IV or oral corticosteroids, and/or UC-related antibiotics through Week 12
- Cyclosporine, tacrolimus, or mycophenolate mofetil (unless for ocular application)
- Cannabis
- Rectal therapy with any therapeutic enemas or suppositories, with the exception of those required for endoscopy
- Apheresis
- Any parenteral nutrition
- Any investigational agent
- Any fecal microbial transplant

## Vaccines

Live or attenuated vaccines are prohibited within 35 days prior to Baseline, during the study, and for 84 days after the last dose of study drug. Vaccines recommended by local guidelines should be considered. If the Investigator chooses to administer a vaccine, this should be completed before first dose of study drug with appropriate precautions and time interval. It is recommended that subjects be up to date for recommended inactivated, toxoid or biosynthetic vaccines, such as injectable flu vaccine, pneumococcal, and pertussis (tetanus, diphtheria, pertussis vaccine [Tdap]).

## 5.4 Prior and Concomitant Therapy

---

Subjects taking oral aminosalicylates, immunomodulators, oral corticosteroids, and/or UC-related antibiotics at Baseline must continue their concomitant treatment for the duration of the induction period (through Week 12). Initiating and/or increasing doses of oral aminosalicylates, immunomodulators, oral corticosteroids, and/or UC-related antibiotics during the study is prohibited through Week 12. Decreasing doses of oral aminosalicylates, immunomodulators, oral corticosteroids, and/or UC-related antibiotics during the induction period is prohibited, except in the event of moderate-to-severe treatment related toxicities and after discussion with the AbbVie TA MD. Starting at Week 12 (maintenance period), oral aminosalicylates, immunomodulators, and/or UC-related antibiotics may be decreased or discontinued at the discretion of the Investigator. Starting at Week 12, initiating and/or increasing doses of oral aminosalicylates, immunomodulators, oral corticosteroids, and/or UC-related antibiotics is permissible after discussion with the AbbVie TA MD.

During the maintenance period, subjects can initiate an optional steroid taper at Week 12. While stopping the taper is permitted, increasing doses above the Baseline dose is permitted only after discussion with the AbbVie TA MD. Below is a suggested tapering schedule.

	Dose	Rate
Prednisone (or equivalent)	> 10 mg/day	5 mg/day per week
	≤ 10 mg/day	2.5 mg/day per week
Budesonide	≤ 9 mg/day	3 mg/day per week

Any questions regarding concomitant or prior therapy should be raised to the AbbVie emergency contact. Information regarding potential drug interactions with ravagalimab can be located in the ravagalimab Investigator's Brochure.

## 5.5 Withdrawal of Subjects and Discontinuation of Study Drug or from Study Participation

---

A subject may voluntarily withdraw or be withdrawn from study participation, or be discontinued from study drug, at any time for reasons including, but not limited to, the following:

- Disease progression or lack of response to treatment.

- Clinically significant abnormal laboratory results or AEs, which rule out continuation of the study drug, as determined by the investigator or the AbbVie TA MD.
- The investigator believes it is in the best interest of the subject.
- The subject requests withdrawal from the study. This includes if a subject would like to discontinue after completion of the Week 52 visit.
- Eligibility criteria violation was noted after the subject started study drug and continuation of the study drug would place the subject at risk.
- Introduction of prohibited medications or dosages and continuation of the study drug would place the subject at risk.
- The subject becomes pregnant while on study drug.
- Subject has a malignancy, except for localized non-melanoma skin cancer. Discontinuation for carcinoma in situ of the cervix is at the discretion of the Investigator.
- Subject is significantly noncompliant with study procedures, which would put the subject at risk for continued participation in the trial.

Subjects who complete the induction period and do not achieve clinical response per Partial Adapted Mayo score at Week 12 will be discontinued.

For subjects to be considered lost to follow-up, reasonable attempts must be made to obtain information on the subject's final status. At a minimum, 2 telephone calls must be made and 1 certified letter must be sent and documented in the subject's source documentation.

AbbVie may terminate this study prematurely, either in its entirety or at any site. The investigator may also stop the study at his/her site if he/she has safety concerns. If AbbVie terminates the study for safety reasons, AbbVie will promptly notify the investigator.

During states of emergency or pandemic situations, it may be necessary to employ mitigation strategies to enable the investigator to ensure subject safety and continuity of care. Acceptable mitigation strategies are identified and included in the Operations Manual in [Appendix F](#).

The investigator should contact the sponsor medical contact before discontinuing a subject from the study for a reason other than "planned per protocol," to ensure all acceptable mitigation steps have been explored.

## 5.6 Follow-Up After Subject Discontinuation of Study Drug or from Study Participation

---

To minimize missing data for efficacy and safety endpoints, subjects who prematurely discontinue study drug treatment should continue to be followed for all regularly scheduled visits, unless subjects have decided to discontinue the study participation entirely by withdrawal of informed consent, in which no further study procedures or study activities can be performed. Subjects should be advised on the continued scientific importance of their data even if they discontinue treatment with study drug early.

If a subject prematurely discontinues from the study/study drug, the procedures outlined for the Premature Discontinuation visit (PD visit) should be completed as soon as possible, preferably within 2 weeks. In addition, if subject is willing, an 84-day follow-up visit after the last dose of study drug may be completed to ensure all treatment-emergent AEs/serious adverse events (SAEs) have been resolved.

If a subject withdraws from study follow up or withdraws permission for the collection of their personal data, the study staff may still use available public records to obtain information about survival status only, as appropriate per local regulations.

In the event a subject withdraws consent from the clinical study, biomarker research will continue unless the subject explicitly requests analysis to be stopped. When AbbVie is informed that samples are withdrawn from research, samples will not be analyzed, no new biomarker analysis data will be collected for the withdrawn subject or added to the existing data or database(s), and the samples will be destroyed. Data generated for biomarker research before subject withdrawal of consent will remain part of the study results.

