Investigational Plan:	
Study M15-722 is a Phase 2a, multicenter, single arm, open-label study to investigate the efficacy and safety of ravagalimab in subjects with moderate to severe UC who failed prior therapy. The study contains a 35-day screening period, 2 treatment periods, and an 84-day follow up period from the last dose of study drug. The induction period is an open-label (OL) 12-week treatment period to evaluate the efficacy, safety, tolerability, pharmacokinetics (PK) and receptor occupancy (RO) of ravagalimab for inducing endoscopic improvement at Week 8. Subjects who achieve clinical response per Partial Adapted Mayo score at Week 12 may continue into the maintenance period. The maintenance period is an OL 92-week treatment period to assess efficacy and safety for maintenance of response with ravagalimab. An internal data monitoring committee (DMC) will review safety at regular intervals.

Key Eligibility Criteria:	
 
Subjects must understand and personally voluntarily sign and date an informed consent, approved by an independent ethics committee (IEC)/institutional review board (IRB), prior to the initiation of any screening or study-specific procedures.
 
Adult male or female, between 18 and 75 years of age, inclusive, at time of the Baseline visit.
 
Diagnosis of UC for at least 3 months prior to Baseline. Appropriate documentation of biopsy results consistent with the diagnosis of UC in the assessment of the Investigator, must be available.
 
Subject meets the following disease activity criteria: Active UC with an Adapted Mayo score of 5 to 9 points and endoscopic subscore of 2 to 3 (confirmed by central review).
 
History of inadequate response, loss of response, or intolerance to one or more of the approved therapies: infliximab, adalimumab, golimumab, vedolizumab, ustekinumab and/or tofacitinib. Dose and duration requirements are specified in Section 5.1.
 

Study Drug and Duration of Treatment:	Ravagalimab (100 mg/mL) Induction Period: 
 
OL ravagalimab 600 mg intravenous (IV) Week 0; ravagalimab 300 mg subcutaneous (SC) Weeks 2, 4, 6, 8, and 10
 
 Maintenance Period: 
 
Open-label ravagalimab 300 mg SC every other week (eow) from Week 12 to Week 102
 

Date of Protocol Synopsis:	04 December 2020

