## 4 INVESTIGATIONAL PLAN

### 4.1 Overall Study Design and Plan

---

Study M15-722 is a Phase 2a, multicenter, single arm, open-label (OL) study to investigate the efficacy and safety of ravaglimab in subjects with moderate to severe UC who failed prior therapy. The study contains a 35-day screening period, 2 treatment periods, and an 84-day follow up period from the last dose of study drug. The induction period is an open-label 12-week treatment period to evaluate the efficacy, safety, tolerability, PK and RO of ravaglimab for inducing endoscopic improvement at Week 8. Subjects who achieve clinical response per Partial Adapted Mayo score at Week 12 may continue into the maintenance period. The maintenance period is an OL 92-week treatment period to assess efficacy and safety for maintenance of response with ravaglimab.

Prior to protocol version 4.0 the study had a double-blind (DB) placebo-controlled induction period. Ongoing subjects enrolled prior to version 4.0 continued their treatment as randomized during the induction period and, in case of clinical response at Week 12, their OL treatment during the maintenance period.

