## 6.2 Toxicity Management

---

The management of specific AEs and laboratory parameters is described in [Table 2](#).

The toxicity management of AEs including AEs of special interest consists of safety monitoring (review of AEs on an ongoing basis, and periodical/ad hoc review of safety issues by a DMC), interruption of study drug dosing with appropriate clinical management if applicable, and discontinuation of the subjects from study drug. There are no time limits for study drug interruption as long as no permanent study discontinuation criteria have been met. The management of specific AEs and laboratory parameters is described below.

For subjects who discontinue study drug but continue study participation and are on standard of care therapies, these toxicity management requirements do not apply (including alerts from the central lab) and any intolerance to standard of care therapies should be managed by the prescribing physician.

**Serious Infections:** Subjects should be closely monitored for the development of signs and symptoms of infection during and after treatment with study drug. Study drug should be interrupted if a subject develops a serious infection or an opportunistic infection. A subject who develops a new infection during treatment with study drug should undergo prompt diagnostic testing appropriate for an immunocompromised subject. As appropriate, antimicrobial therapy should be initiated, and the subject should be closely monitored. Study drug may be restarted once the infection has been successfully treated or resolved. Subjects who develop active TB or experience Hepatitis B reactivation must be discontinued from study drug. For subjects who develop TB during the study, the supplemental eCRF should be completed.

**COVID-19:** Interrupt study drug in subjects with a confirmed diagnosis of COVID-19. Consider interrupting study drug in subjects with signs and/or symptoms and suspicion of COVID-19. The COVID-19 eCRF must be completed. If a subject has a confirmed or suspected SARS-CoV-2 infection and study drug was interrupted, the investigator should contact the AbbVie TA MD before reintroducing study drug.

**Malignancy:** Subjects who develop malignancy other than NMSC or carcinoma in situ of the cervix must be discontinued from study drug. Information including histopathological results should be queried for the confirmation of the diagnosis. The supplemental eCRF should be completed.

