## 3.13 Subject Withdrawal from Study

---

All attempts must be made to determine the primary reason for discontinuation of study drug or study participation. The information along with the date of the last study drug dose will be recorded on the appropriate eCRF page. However, these procedures should not interfere with the initiation of any new treatments or therapeutic modalities that the investigator feels are necessary to treat the subject's condition. Following discontinuation of study drug, the subject will be treated in accordance with the investigator's best clinical judgment, irrespective of whether or not the subject decides to continue participation in the study.

If a subject withdraws from the main study, biomarker research samples will continue to be stored and analyzed. A subject must contact the Investigator if they no longer want their samples to be stored and analyzed. Once AbbVie is notified, no new information will be collected, no new analysis will be started, and the samples will be destroyed unless a regulatory authority requires AbbVie to keep them. However, if AbbVie (or people or companies working with AbbVie) collected any information or did any testing before withdrawal, AbbVie (or people or companies working with AbbVie) will still use and disclose such information, use the test results, and keep the data generated from the samples.

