8.0 Efficacy Analyses

8.1 General Considerations

UC-Related corticosteroids intercurrent events are defined as follows:

- subjects not on UC-related corticosteroids (systemic or locally acting corticosteroids for UC) at Baseline who initiated UC-related corticosteroids during the Induction Period;
- subjects on UC-related systemic corticosteroids at Baseline who had dosages increased to greater than the prednisone equivalent dose of corticosteroid at Baseline, or initiation of any rectal corticosteroids during the Induction Period regardless of rectal corticosteroid dose.

The time point of the UC-related corticosteroids intercurrent event is defined as the date when one of the scenarios above occurs for a subject. As such, subjects will be considered as "non-responder" for binary endpoints at or after the occurrence of the UC-related corticosteroids intercurrent event through the end of the Induction Period. For continuous endpoints, all measurements at or after the occurrence of the UC-related corticosteroids intercurrent event through the end of the Induction Period will not be used in the analysis.

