8.2 Handling of Missing Data

Missing data imputation will be done only for efficacy variables (categorical and continuous variables). For the analysis other than efficacy, no imputation will be done for missing values.

Censoring

For the time-to-event endpoint, i.e., time to clinical response per Partial Adapted Mayo score, missing data will be considered as censored at the last available time for the information.

Non-Responder Imputation incorporating Multiple Imputation to handle missing data due to COVID-19 (NRI-C)

The NRI-C will categorize any subject who does not have an evaluation during a pre-specified visit window (either due to missing assessment or due to early withdrawal from the study) as a non-responder for the visit. In addition, at or after the UC-related corticosteroids intercurrent event (see Section 8.1), subjects will be counted as non-responders. The only exception is that missing data due to COVID-19 infection or logistical restrictions related to the COVID-19 pandemic will be handled by Multiple Imputation (MI). At each visit, subjects will be characterized as responders or non-responders based on MI imputed values if missing due to COVID-19; otherwise, subjects will be considered as non-responders for missing due to other reasons in the NRI-C approach.

Mixed-Effect Model Repeated Measurements (MMRM)

MMRM analysis will be conducted using mixed-effect model including observed measurements at all visits. For the MMRM analysis, data collected at or after UC-Related corticosteroids intercurrent event will be excluded. The mixed model includes the categorical fixed effects of visit, baseline corticosteroid use (yes vs no), baseline Mayo endoscopic sub-score (2 vs 3), the continuous fixed covariate of baseline measurement and treatment and treatment-by-visit interaction, if applicable. An unstructured variance covariance matrix will be used. If there is a convergence issue, a compound symmetry structure and a variance components structure will be considered in sequence. The parameter estimations are based on the assumption of data being missing at random and using the method of restricted maximum likelihood (REML).

As Observed (AO)

The AO analysis will not impute values for missing evaluations, and thus a subject who does not have an evaluation on a scheduled visit will be excluded from the AO analysis for that visit. All observed data will be used in the analysis.

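### SAP 8.5 counts every observed maintenance result as a ravagalimab result, with no rule for subjects who have stopped the drug or added UC therapy

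*Protocol*

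**What the plan says.** The Protocol Synopsis gives the aim of the second treatment period: "The maintenance period is an OL 92-week treatment period to assess efficacy and safety for maintenance of response with ravagalimab".

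For subjects who stop study drug, Protocol 5.6 asks that "subjects who prematurely discontinue study drug treatment should continue to be followed for all regularly scheduled visits", unless consent is withdrawn. Protocol 6.2 has a provision that begins "For subjects who discontinue study drug but continue study participation and are on standard of care therapies", so it foresees other treatment during continued participation. Operations Manual 3.13 (Protocol Appendix F) says: "Following discontinuation of study drug, the subject will be treated in accordance with the investigator's best clinical judgment", whether or not the subject stays in the study.

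For subjects still on study drug, Protocol 5.4 states: "Starting at Week 12, initiating and/or increasing doses of oral aminosalicylates, immunomodulators, oral corticosteroids, and/or UC-related antibiotics is permissible", after discussion with the sponsor's medical director.

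On the analysis side, SAP 8.5 gives descriptive maintenance summaries for the ravagalimab group, using AO data for both binary and continuous endpoints. SAP 8.2 says of AO: "All observed data will be used in the analysis". SAP 4.0 defines the Full Analysis Set by receipt of at least one ravagalimab dose. SAP 8.1 defines one intercurrent event, UC-related corticosteroid use, and treats subjects as non-responders "at or after the occurrence of the UC-related corticosteroids intercurrent event through the end of the Induction Period".

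**The concern.** The study has a single arm, so a maintenance rate reported for ravagalimab will be read as what the drug sustains. Under the planned rule, a subject who stops ravagalimab, is treated with something else and is in remission at Week 52 counts as a responder in the ravagalimab row. So does a subject who stays on ravagalimab but starts corticosteroids after Week 12. In induction the SAP would score that second subject as a non-responder. In maintenance it has no rule, and maintenance is when adding or increasing these therapies becomes permissible.

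At stake is what the Week 52 and Week 104 rates mean. As planned they describe a mixture of therapies, and nothing in the tables would tell a reader how large the mixture is.

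**Working it through.** **Does any rule separate these subjects?** Each place where one could stand was checked.

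- Population (SAP 4.0): at least one dose of ravagalimab, with no on-treatment condition.
- AO definition (SAP 8.2): drops missing evaluations only. It does not refer to stopping drug or starting other therapy.
- Intercurrent events (SAP 8.1): corticosteroids only, and only to the end of induction.
- Prohibited therapy (Protocol 5.3): other UC biologics and small molecules are barred throughout the study. This governs conduct. SAP Appendix A counts breaches as deviations and does not remove or reclassify the results.
- Steroid endpoints (Protocol 3.4, SAP 3.3): these cover subjects on corticosteroids at Baseline who later stopped them. They do not cover new starters or switchers.

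No rule was found.

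**Who is affected?** Mainly subjects who entered maintenance and later stopped ravagalimab or added UC therapy. Week 12 non-responders are discontinued with an 84-day follow-up contact (Protocol 4.1), so they fall largely outside the problem.

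**How large could it be?** The plan states no maintenance rate, so there is no figure to reproduce. The documents also do not give the number entering maintenance, the number stopping drug while still attending, or their response on other therapy. All three are assumed below.

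Let M be the subjects observed at Week 52, k those off drug, r the responders on drug, and p the response rate among those off drug.

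- AO rate = (r + k × p) / M
- Stopping counted as non-response = r / M
- On-drug subjects only = r / (M − k)
- AO minus stopping-as-non-response = k × p / M

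Take M = 20, an on-drug response of 50%, and p from 0 to 1:

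| k | r / (M − k) | Stopping as non-response | AO rate | AO excess, points |
|---|---|---|---|---|
| 2 | 9/18 = 50% | 9/20 = 45% | 45% to 55% | 0 to 10 |
| 4 | 8/16 = 50% | 8/20 = 40% | 40% to 60% | 0 to 20 |
| 6 | 7/14 = 50% | 7/20 = 35% | 35% to 65% | 0 to 30 |
| 8 | 6/12 = 50% | 6/20 = 30% | 30% to 70% | 0 to 40 |

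On the same observed subjects, the AO rate is never below the stopping-as-non-response rate. It can lie on either side of the on-drug rate. For example, suppose 12 subjects are on drug with 6 responding, 8 have stopped, and 5 of those 8 attend with 2 responding. Then AO = (6 + 2)/(12 + 5) = 8/17 = 47%. Counting stopping as non-response gives 6/17 = 35%, and on-drug subjects alone give 6/12 = 50%.

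**The case against.** The strongest reply is that this is a descriptive summary in an exploratory study. The objective is to explore, the primary endpoint is at Week 8, the key secondary endpoints belong to induction, and the maintenance endpoints are additional, with no hypothesis or decision rule. All of this stands. It limits the weight of the point, but it does not say whose treatment the rates describe.

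A second reply is that following subjects off drug is good practice and that an all-observed summary is a recognised treatment-policy approach. The follow-up is sound and should stay. However, the SAP does not call AO a treatment-policy summary, and in induction it scores corticosteroid use as non-response.

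Third, Protocol 5.3 prohibits other biologics and small molecules throughout the study, and Protocol 6.2 does not predict that stopped subjects will receive other therapy; it only exempts those who do from the toxicity rules. That is correct, and the frequency is unknown. Protocol 5.3 still fits poorly with 6.2 and Operations Manual 3.13. New steroids and immunomodulators after Week 12 are not prohibited; 5.4 allows them after discussion with the sponsor.

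Fourth, it is not fully clear whether stopped subjects have the scheduled endoscopies as well as the one at premature discontinuation, because Operations Manual 3.15 writes Week 104 and premature discontinuation as a pair. This may reduce the effect on endoscopic endpoints. It does not remove the effect on Partial Adapted Mayo endpoints, which are assessed at every maintenance study visit from Week 16 in Appendix D.

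A reader might infer that the maintenance data cannot show maintenance of response at all, or that the AO rate must flatter ravagalimab. The documents support neither. The effect is zero if no stopped subject attends or none who attends responds. Stopped subjects who attend and fail lower the AO rate: in the example, 47% is below the on-drug 50%.

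**Conclusion.** The gap is real but limited. From Week 12 the SAP has no rule for results obtained after ravagalimab is stopped or UC therapy is added, so the Week 52 and Week 104 binary rates can mix therapies under the ravagalimab label. The Week 8 primary endpoint is not touched.

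Against a rate that counts stopping as non-response, the AO excess equals the share of observed subjects who respond off drug. The ranges of 0 to 10 points (2 of 20 off drug) up to 0 to 40 points (8 of 20) rest on assumed counts, with all 20 subjects observed. Responses after added therapy on study drug would come on top and cannot be sized from the documents. Against an on-drug rate the direction is open. What the plan lacks is a stated choice between these quantities and the counts needed to interpret the one it reports.

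**What to change.** Make these changes in SAP 8.1 and 8.5:

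- For maintenance binary endpoints, count a subject as a non-responder from permanent discontinuation of ravagalimab, from the start of another UC biologic or small molecule, or from a UC-related corticosteroid event as SAP 8.1 already defines it for induction. Use the earliest of these.
- Report new immunomodulator starts as a sensitivity analysis, since the induction rule names corticosteroids only.
- Present this table over the subjects who entered maintenance, and state how missed visits count in that denominator.
- Keep the AO table as a labelled supplement with on-drug and off-drug counts at each visit.
- For continuous endpoints, keep the AO summaries and show on-drug and off-drug values separately. Only excluding later values would leave a selected on-drug group.

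Protocol 5.3 must also be reconciled with Protocol 6.2 and Operations Manual 3.13 on therapy after study drug is stopped. This review takes no position on which should prevail.

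The cost is SAP wording and one extra table set. The last-dose date is already recorded (Operations Manual 3.13), and concomitant therapy is already reviewed at maintenance study visits (Appendix D). Reported maintenance rates may be lower.
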